10.0 Adverse Event Reporting

It is the responsibility of the investigator to document all treatment related and device related Adverse Events (AE's), which occur during the course of the study. At each visit, the investigator will evaluate AE's. AE's not previously documented in the study will be recorded on the Adverse Event Log within the subject's CRF. The nature of each event, date and time (when appropriate) of onset, outcome, frequency, maximum intensity, action taken, and attribution will be recorded. AEs already documented in the CRF (i.e., at a previous assessment) and designated as 'ongoing', should be reviewed at subsequent visits as necessary. If these have resolved, the documentation in the CRF should be completed including an end date for the event.

If an AE increases in frequency or severity during a study period, a new record of the event will be started.

Standard Code of Federal Regulation (CFR) definitions for Serious Adverse Events (SAEs) will be used for evaluation of adverse events.

SAE [§803.3(aa)(1)] is an injury or illness that:

- *causes death*
- *is life threatening, even if temporary in nature;*
- *results in permanent impairment of a body function or permanent damage to a body structure; or*
- *necessitates medical or surgical intervention to preclude permanent impairment of a body function or permanent damage to a body structure.*

All AEs (related or unrelated) meeting the criteria for an SAE require notification of the sponsor and the reviewing IRB as soon as possible, with subsequent completion of additional paperwork provided by the sponsor fully documenting the course of the event, all treatments, and final outcome. Initial reporting of an SAE should be made to the sponsor no later than two (2) working days after the PI learns of the incident.

Standard Code of Federal Regulation (CFR) definitions for Unanticipated Adverse Device Effects (UADEs) will be used for evaluation of this type of adverse event.

UADE [§812.3(s)] means any serious adverse event on health or safety or any life-threatening problem or death caused by, or associated with, a device, if that effect, problem, or death was not previously identified in nature, severity, or degree of incidence in the investigational plan or application (including a supplementary plan or application), or any other unanticipated serious problem associated with a device that relates to the rights, safety, or welfare of subjects.

Any UADEs will be reported to InSightec through the eCRF and to the reviewing IRB as soon as possible. However, in no event must this report be made later than two (2) working days after the PI learns of the incident.

Other common non-study or non-device related, minor health complaints will not be collected as AEs (for example: colds, sprains, headaches). Subjects who have a progression of their primary disease or symptoms that lead to an alternative treatment will not be reported as an AE.

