3.1 Safety

The safety of Exablate lesioning of the bilateral medial thalamus using the ExAblate device will be determined by an evaluation of the incidence and severity of device- and procedure-related complications from the first / treatment day visit through the post-treatment visits. Safety analysis will also include monitoring for any worsening of pain related to painful PN. Events that are neither device- nor procedure-related will be captured and recorded but will not be considered reportable device events unless caused by the device. Relative Safety will be evaluated using a common description of Significant Clinical Complications for patients treated in this study.

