3.2 Efficacy

Outcome assessments will primarily be made at baseline, one, and three months post procedure for patients receiving either the active treatment or sham procedure. Clinical assessments of pain will be made at all clinic visits.

Primary outcome: **safety** as assessed from adverse event reporting and MRI evaluation

Primary efficacy outcome measure will compare the change of **WORST** pain experienced in 24 hours before and at 3 months following bilateral FUS medial thalamotomy versus sham procedures as determined from the 11-point numeric pain rating scale.

Secondary outcome measures will include other patient-reported outcomes including the Global Impression of Change and the Pain Domain from the PROMIS Inventory including items for intensity, quality, behavior and interference.

Imaging assessments will be obtained before and after treatment. The location and precision of the treatment, as well as the volume of the lesion, will be determined from pre- and posttreatment MRI at baseline, 1 day, 1 week, 1 month and 3 months. Functional imaging assessments with Dynamic 2-[¹⁸F] fluoro-2-deoxy-D-glucose Positron Emission Tomography (FDG PET) will be obtained at baseline and three months for each patient. Functional imaging will serve as an objective measure to correlate with clinical pain assessment.

A summary of outcome measures is listed:

Primary (efficacy) outcome: 11-point numeric pain rating scale NPRS (“worst” NPRS score over 24 hours). The change in pain rating from baseline to 3 months posttreatment will be determined and compared between treatment and control cohorts.

Secondary outcomes:

Patient-reported outcome measures:

- PROMIS scale v1.0 – Pain Intensity 3a
- PROMIS scale v2.0 – Neuropathic Pain Quality 5a
- PROMIS scale v2.0 – Nocioceptive Pain Quality 5a
- PROMIS scale v1.0 – Pain Behavior 7a
- PROMIS scale v1.0 – Pain Interference 8a
- Patient Global Impression of Change, 7 point

Functional imaging assessments:

- Dynamic FDG PET

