8.1 Safety

All adverse events will be recorded and categorized according to severity, relationship to procedure and relationship to device. Any subject who receives at least one sonication will be considered Intent to Treat (ITT) for safety assessments. All AEs will be assessed for their relationship to the study device or procedure. Standard Code of Federal Regulation definitions for Serious Adverse Events (SAEs) and Unanticipated Adverse Device Effects (UADEs) will be used in assessment of AEs.

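### Section 10.0 keeps symptom progression that leads to alternative treatment out of adverse event reporting, although Section 3.1 counts worsening pain as a safety matter and safety is the primary outcome

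*Protocol*

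**What the plan says.** Section 3.2 makes safety the primary outcome, "as assessed from adverse event reporting and MRI evaluation". Section 3.1 adds two commitments: "Safety analysis will also include monitoring for any worsening of pain related to painful PN", and "Events that are neither device- nor procedure-related will be captured and recorded". Section 8.1 says "All adverse events will be recorded and categorized according to severity, relationship to procedure and relationship to device". Sections 9.8 and 9.9 also send events of any cause to the case report form (CRF) and then assess cause, with unrelated as one of the options. Section 10.1 has the Data Safety Monitoring Board (DSMB) review all AEs and decide whether each is related to the device.

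Section 10.0 opens differently: "It is the responsibility of the investigator to document all treatment related and device related Adverse Events". It then has new events logged at each visit with their attribution, and for serious events it states "All AEs (related or unrelated) meeting the criteria for an SAE require notification of the sponsor and the reviewing IRB". It closes with two exclusions. Common complaints unconnected with the study or device fall under the first: "minor health complaints will not be collected as AEs". The second reads: "Subjects who have a progression of their primary disease or symptoms that lead to an alternative treatment will not be reported as an AE".

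Section 9.5 puts increased pain within the first of the primary risks of the bilateral lesion. Section 9.8.1 lists dysesthesias and pain among the neurological deficits reported to date.

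**The concern.** In a pain trial, worsening of the presenting symptom is both a possible course of the disease and a named risk of the lesion. The progression sentence in Section 10.0 does not separate the two. It has no relatedness qualifier, so a worsening caused by the procedure can be called progression and left out of the AE record once it leads to another treatment. Under Section 6.4 the neurosurgeon and the clinical research coordinator know the arm, so the person who makes that call may not be blinded.

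What would be lost is the severity grade, the attribution and the DSMB's own judgement of cause, for a kind of event that bears directly on the primary outcome. The remaining wording in Section 10.0 adds a smaller problem: staff who follow its opening sentence and its minor-complaints exclusion may record different non-serious events from staff who follow Section 3.1 or 8.1.

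**Working it through.** The protocol states no figure on this point, so the check is mainly a comparison of passages.

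**Progression sentence against the safety sections.**

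| Section | Treatment of worsening pain |
|---|---|
| 3.1 | any worsening belongs to the safety analysis |
| 9.5, 9.8.1 | increased pain, or dysesthesias and pain, is a procedure risk |
| 10.0, opening | treatment-related events are documented |
| 10.0, last sentence | progression leading to alternative treatment is not an AE, whatever the cause |

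I read the painful PN of Section 3.1 as the facial pain under study. On that reading the last row cannot be applied together with the first three when the worsening is treatment-related and the subject moves to another treatment. Section 10.0 does not define alternative treatment. Section 6.7 uses the term with medication changes excepted; Section 10.0 has no such exception, so the width of the exclusion is itself unclear.

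**What else would catch the event.**

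- The numeric pain rating scale (NPRS) is completed at every follow-up visit (Sections 6.7 and 7.0). It shows the score, not severity as an AE, cause or DSMB review.
- Under Section 6.7 a subject who uses alternative treatment leaves the study after the required examinations, and the reason goes on the CRF. That is a trace, but not an AE.
- Section 9.11 halts the study for evaluation if two or more subjects have a 50% rise in pain from baseline at two consecutive visits. It does not name the scale. Assume worst NPRS, 0 to 10, with entry at 5 or more (Section 5.2). The score needed is 1.5 × baseline:
  - baseline 5: 1.5 × 5 = 7.5, so 8 on whole numbers;
  - baseline 6: 1.5 × 6 = 9;
  - baseline 7: 1.5 × 7 = 10.5, which is off the scale.

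  Under that assumption, subjects who start at 7 or more can never meet the rule.

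**Size.** Ten subjects randomized 1:1 (Section 8.4) give 10 / 2 = 5 per arm. The documents give no rate for such events, so I show the effect of one, as an assumption. Omitting it from the treated arm changes the AE table from 1/5 (20%) to 0/5 (0%).

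**Opening sentence and minor complaints.** The opening of Section 10.0 names related events. Sections 8.1, 9.8, 9.9 and 10.1 start from all events and settle relationship afterwards. The minor-complaints sentence says certain unrelated events are not collected; Section 3.1 says unrelated events are recorded. Headache shows the practical difficulty: Section 10.0 gives it as an example of a complaint not collected when unrelated, while Section 9.8.1 lists it as procedure-related. Whether it is logged then depends on a judgement of cause made before the DSMB sees it.

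**The case against.** The best defense is that the progression sentence concerns the underlying disease, whereas the pain in Sections 9.5 and 9.8.1 comes from lesion spread or damage to nearby structures. Such pain is a new, treatment-related event that the opening of Section 10.0 requires to be documented. This stands in part: the sentence does not name lesion-caused pain, and a careful investigator could record it. But it covers symptoms as well as disease, gives no test for telling them apart, and is applied before the DSMB's review.

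The other safeguards are real, so it would be wrong to infer that worsening pain disappears from the study. Scores, exit reasons and the Section 9.11 rule remain.

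A reader might also infer that Section 10.0 restricts recording to related events. The text does not support that. The opening sentence does not say only, the section goes on to record attribution, and excluding minor unrelated complaints would be redundant if every unrelated event were already out. Sections 8.1, 9.8 and 10.1 speak of all AEs without defining the term, so they can be read alongside Section 10.0. The direct textual conflict is between the minor-complaints sentence and Section 3.1, and either could be amended.

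Two further inferences should be resisted. Section 9.8 remarks that related events arise within 30 days, but this is a description and not an attribution rule, so it does not show that later events go unrecorded. And Section 8.2 removes subjects with a significant pain-medication change from the efficacy analysis. To argue that such a subject vanishes from both analyses requires a medication change and an excluded progression in the same person, which is a compound hypothetical.

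**Conclusion.** The concern holds for the progression sentence. As written, it allows a treatment-related worsening of facial pain to be left out of AE reporting, against Section 3.1, in a trial whose primary outcome rests on that reporting. The exposure is limited to worsening that leads to alternative treatment, and other records capture part of it. One omitted event, which is an assumption and not an estimate, moves a treated arm of 5 from 20% to 0%. The statement that Section 9.11 cannot be reached from a baseline of 7 or more rests on reading pain there as worst NPRS.

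The opening sentence and the minor-complaints exclusion are secondary: one is ambiguous, the other conflicts with Section 3.1, and both affect non-serious events only, since serious events are notified whether related or not. The point should be fixed, but it does not undermine the design.

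**What to change.** In Section 10.0:

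1. Delete or amend the progression sentence, so that post-procedure worsening of facial pain is recorded as an AE with severity and attribution, in both arms, whether or not it leads to alternative treatment.
2. Reword the first sentence to: *document all adverse events in both arms, whatever their attribution*. Relationship is then assigned afterwards, as in Section 8.1, and reviewed by the DSMB, as in Section 10.1.
3. Reconcile the minor-complaints sentence with Section 3.1 by amending either passage.

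The cost is a wording change, matching CRF guidance and a few more AE log entries in 10 subjects. The change does not alter who knows the arm; it lets the DSMB see the event before its cause is settled.

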10.1 Adverse Events Analysis

A Data Safety Monitoring Board will be used to review all AE's on the study. Their role is to evaluate all AE's that occur throughout the study and determine if they are in fact related to the ExAblate, or some other cause. We would closely monitor all treatments for any AE's, and consider the following questions for AEs in the Test Arm:

- *Was the adverse event serious?*
- *life-threatening, caused a disability: required or prolonged hospitalization: caused death.*

- *Was the adverse event device related?*
- *Was the adverse event unexpected?*
- *Is there an unreasonable risk in continuing the trial?*

If in fact it is determined that an ExAblate-treated subject experienced an AE that met all of the above criteria, we would stop the trial pending further investigation. If in the opinion of the DSMB, a modification of the study protocol were necessary to provide adequate protection to future study participants, the modification would be implemented prior to reinitiating the investigation. Any such amendment would be reported to the IRB and FDA as required by the applicable regulations.

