9.4 Risks Associated with the MRgFUS Treatment

- There is a potential risk of hemorrhage during MRgFUS treatment. In MRgFUS thermal ablation, the high temperature at the focal point results in immediate protein denaturation and coagulative necrosis. This should be expected to rapidly stop any bleeding that might occur in the capillary bed and within small vessels. At the end of the MRgFUS procedure an unenhanced MR scan is performed to assess the treated area and adjacent tissues.
- There is a risk of discomfort to the subject caused by heating of tissue. Focused ultrasound therapy involves precisely controlled pulses of thermal energy resulting in tissue coagulation (typically 55-65°C for several seconds) in small tissue volumes. This induces thermal coagulation of the targeted soft tissue. The energy intensity at the level

of the skin is quite low, and there should be no local heating, hence no sensation of pain at the scalp. The rise in temperature in the skull should be kept to below pain level by active cooling of the water within the rubber diaphragm. Because the focal point of the beam will be > 2.5 cm from the dura and there are no pain receptors in the brain, there should be no pain associated with ablation. The subject will be in verbal contact with the physician and appropriate action can be taken in the event that a subject does experience discomfort. Remedies could involve lowering energy levels, increasing the time interval between consecutive treatment pulses, or increasing the level of sedation and/or analgesia. The subject also has the ability to abort the sonication at any time by activating a handheld cut off circuit (i.e., stop switch).

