9.5 Risks related to bilateral lesioning of central lateral thalamic nucleus

We perceive the following primary risks of bilateral FUS medial thalamotomy based on our review of the historical literature of medial thalamotomy, the extensive experience of CL thalamotomy by our colleague Jeanmonod, and our experience with FUS Vim thalamotomy for ET:

1. Somatosensory deficit & increase pain – from lateral extension of the lesion to VPL
2. Transient cognitive disturbance or confusion
3. Hemorrhagic morbidity – from thermal ablation
4. Cavitation – from focused ultrasound

Somatosensory deficit & increased pain.

Medial thalamic lesions target the intralaminar nuclei and do not result in discriminative somatosensory deficits. Historical lesion of the lateral thalamus (VPM/VPL) often resulted in somatosensory deficits and increased pain due to deafferentation. In order to mitigate this risk, medial thalamic lesions will be confined to the CL nucleus and will not extend laterally to the VPM. The laterality of the coordinates for medial thalamic lesions will be maintained less than 10 mm.

The thermal lesioning process with focused ultrasound could cause **neurological effects** for several reasons. Any effects outside of the treatment area could result in neurologic signs or symptoms. These could occur from the thermal lesioning process that is 'off-target' or

associated infarction, hemorrhage or edema. Subjects will be observed and monitored during the treatment for signs of neurologic side effects. They will also be observed overnight on the neurosurgical ward. Most neurologic side effects would manifest within minutes to hours. Those related to cerebral edema will be transient and expected to resolve within 2-3 weeks.

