- Mis-alignment, mis-targeting or reflection of the ExAblate beam.
- Heating of structures in the FUS backbeam or forebeam
- Additionally, the following side effects are thought to be improbable but their relative risks remain to be defined:

Scalp in the sonication pathway:	Dura, venous sinuses, and cortical veins

 Skin burns ($>2^{\circ}$) with ulceration of the skin Scar formation Loss of sensation Atrophy 	
 Subdural bleeding Vein thrombosis Cortex heating Seizures Symptoms from disturbances of eloquent cortical areas (motor, sensory, auditory, visual, speech)
Bone in the sonication pathway:	

 Bone necrosis 	
Other brain tissue	Cerebral arteries

 Necrosis of normal tissue due to incorrect targeting Thermal damage to adjacent functional brain tissue (e.g.: optical tract) Bleeding in the treated area Cerebral infarction Moderate or severe increase in cerebral edema as shown by MRI scans Symptomatic increase of intracranial pressure Death 	
 Bleeding Coagulation thrombosis Vasospasm Death

Adverse events will be assessed for their relationship to the study device or procedure. Standard Code of Federal Regulation (CFR) definitions for SAEs and UADEs will be used in assessment of adverse events.

Focused Ultrasound thalamotomy has previously been described for essential tremor. These thalamotomies for tremor were performed unilateral to the ventral intermediate nucleus, which is located adjacent to the internal capsule and ventral posterolateral somatosensory nucleus of the thalamus. The medial thalamic target for this study will serve as a central lateral thalamus, and immediately positioned intralaminar nucleus that should not incur risks for sensory, motor, or

cerebellar disturbance. This nocioceptive region of the thalamus will be targeted bilaterally. Acoustic energy will be titrated until peak voxel temperatures at the target reach 55 to 65 degrees Celsius. Intraoperative feedback is less important for this target than for tremor monitoring, so subjects can undergo intravenous sedation for comfort without losing localizing clinical feedback. The postoperative care of medial, CL thalamotomy will be the same as those for Vim thalamotomy with a one day hospital stay.

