9.11 Criteria for Stopping the Study

The study will be stopped for evaluation should:

1. any death occur, or
2. if two or more subjects experience
 - a. a cerebrovascular hemorrhage
 - b. or serious related neurological adverse event
 - c. or a 50% increase in pain from Baseline following two consecutive visits starting from 7-days post treatment visit.

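### Because Section 10.1 requires an event to be unexpected, and Section 9.11 requires two subjects, one serious non-fatal event classed as expected obliges no stop even if continuing is judged an unreasonable risk.

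*Protocol*

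**What the plan says.** Two parts of the protocol govern stopping.

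- **Section 10.1 (Adverse Events Analysis)** lists questions to ask of an adverse event in the test arm: whether it was serious, whether it was device related, "Was the adverse event unexpected", and "Is there an unreasonable risk in continuing the trial". The commitment to halt applies when an ExAblate-treated subject "experienced an AE that met all of the above criteria, we would stop the trial pending further investigation". The same section says that "A Data Safety Monitoring Board will be used to review all AE's on the study", with the role of deciding relatedness to the device.
- **Section 9.11 (Criteria for Stopping the Study)** stops the study for evaluation after any death. Otherwise it acts "if two or more subjects experience" a cerebrovascular haemorrhage, a serious related neurological event, or a sustained 50% rise in pain.

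Haemorrhage is named in advance in three places. Section 9.4 says "There is a potential risk of hemorrhage during MRgFUS treatment", Section 9.5 lists "Hemorrhagic morbidity – from thermal ablation" among the primary risks, and Section 9.8 includes "Bleeding in the treated area" in a list of effects thought improbable, whose relative risks are still to be defined.

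Section 10.1 does not define unexpected. The nearest standard is the regulatory definition of an unanticipated adverse device effect (UADE) in Section 10.0, which turns on whether the nature, severity or degree of incidence had been identified beforehand.

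**The concern.** Under Section 10.1 the judgement that matters most, whether it is unreasonable to go on, is not enough to oblige a halt. The event must also have been unforeseen. Listing a hazard in advance does not make it safer for the next subject, so expectedness is a sensible test for expedited reporting but a poor one for stopping.

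The next subject, whether randomized or crossing over from sham, would receive a permanent bilateral thalamic lesion, and the text requires no pause first. If exactly one bleed occurs and is equally likely at any position among *n* sequential treatments, the mean number still to come is (*n* - 1)/2, which is 4.5 of 10.

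**Working it through.** **Step 1. The rules as logic.** The protocol states no figure to reproduce here.

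- Section 10.1 halt = serious AND device related AND unexpected AND unreasonable risk.
- Section 9.11 halt = any death OR at least two subjects with a qualifying non-fatal event.

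Take one subject with a non-fatal, serious, device-related haemorrhage:

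| Unexpected? | Unreasonable risk? | 10.1 obliges halt | 9.11 obliges halt |
|---|---|---|---|
| No | No | No | No |
| No | Yes | **No** | **No** |
| Yes | No | No | No |
| Yes | Yes | Yes | No |

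The second row is the gap. A bleed could count under two items of 9.11, but it is still one subject.

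**Step 2. Do other provisions close it?** Section 10.0 requires serious events to be notified to the sponsor and IRB whatever their expectedness, but that is reporting. DSMB review is not tied to a pause. The DSMB's role in modifying the protocol is described as coming before the investigation is restarted, so it presupposes a halt. Section 9.10 concerns removal of individual subjects. Section 12.0 requires conduct under FDA and ICH-GCP requirements but sets no pause rule.

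**Step 3. How often would a lone bleed arise?** Binomial with independent subjects and *n* = 10 treated, assuming all five sham subjects cross over (Sections 6.2 and 8.4):

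P(0) = (1 - p)^10; P(1) = 10p(1 - p)^9; P(2 or more) = 1 - P(0) - P(1).

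Rates:
- 0.5% is an assumption, within the below-1% figure that Section 2.5 gives for electrode procedures.
- 1% and 2% bound the stereotactic range in Section 9.5, which adds that bleeding is probably slightly more frequent with radiofrequency than with focused ultrasound.
- 1/11 is the one bleed among 11 ablated patients in the focused ultrasound central lateral thalamotomy series in Appendix A.

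| p | P(exactly 1) | P(2 or more) | P(at least 1) | P(only one, given any) |
|---|---|---|---|---|
| 0.5% (assumed) | 4.8% | 0.1% | 4.9% | 97.8% |
| 1% | 9.1% | 0.4% | 9.6% | 95.5% |
| 2% | 16.7% | 1.6% | 18.3% | 91.2% |
| 1/11 | 38.6% | 22.9% | 61.4% | 62.7% |

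Worked line for 1/11: P(0) = (10/11)^10 = 0.3855; P(1) = 10 × (1/11) × (10/11)^9 = 0.3855; P(at least 1) = 1 - 0.3855 = 0.6145; P(2 or more) = 0.6145 - 0.3855 = 0.229 after rounding; ratio = 0.3855/0.6145 = 0.627.

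If no sham subject crosses over (*n* = 5), exactly one bleed has probability 4.8% at 1%, 9.2% at 2% and 31.1% at 1/11. Two or more has 0.1%, 0.4% and 6.9%.

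**Step 4. Limits of these figures.** They describe bleeds, not the gap. The gap also needs the bleed to be serious, device related, non-fatal, classed as expected and judged an unreasonable risk, with no voluntary halt. The protocol gives no rates for those. The 1/11 rate comes from one small series, and its bleed preceded the adoption of cavitation detectors, which this trial's device has (Section 9.4).

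**The case against.** **The case nearly defeats itself.** It needs a responsible body to find that continuing is unreasonable and then to continue. Nothing forbids a discretionary halt, and serious events reach the sponsor within two working days. This stands, and it is why the practical effect is small. A reader might infer that the protocol allows or intends treatment to go on after such a finding. The text does not support that: it only fails to oblige a stop.

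**The bleed may not be classed as expected.** If the UADE wording is borrowed, an event can be unanticipated in severity or degree of incidence. One serious bleed among at most 10 treated is at least 10%, against 1-2% in Section 9.5, and Section 9.8 calls bleeding improbable. Section 10.1 could then apply after one event. This also stands, though an arguable classification should not decide whether a halt is mandatory.

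**The rules may be a deliberate division:** unforeseen events can stop the trial singly, while foreseen ones are counted. That is a coherent reading, and no sentence contradicts another. It does not explain why a foreseen event already judged to make continuing unreasonable should wait for a second subject.

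**The 9.11 count is a real backstop.** A reader of the low-rate rows might infer that it would hardly ever be reached. That does not hold across the protocol's own evidence: at 1/11, two or more bleeds have probability 22.9%. In addition, 9.11 may be met by a second subject with a different qualifying event, which these figures leave out.

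**Conclusion.** The point holds as a narrow matter of drafting. On the text of Sections 10.1 and 9.11, one non-fatal, serious, device-related event classed as expected obliges no stop, even when continuing is judged an unreasonable risk. The cause is the requirement that all conditions in 10.1 be met, combined with the two-subject threshold in 9.11. It would be too strong to say that no single non-fatal event can stop the trial, since an unexpected one meeting the other conditions does.

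A lone bleed is the more likely pattern at every rate considered: if any occurs among 10 treated, it is the only one in 63-98% of cases. This rests on independent subjects, full crossover and rates from 0.5% to 1/11. The probability of the gap itself cannot be computed from the protocol. Because voluntary halting is likely and the classification is open to argument, this is a change to consider rather than a defect that undermines the trial.

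**What to change.** In Section 10.1, remove unexpectedness from the stopping conditions and keep it for UADE reporting under Section 10.0. Replace the stopping sentence with:

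*If an ExAblate-treated subject has a serious, device- or procedure-related AE and the DSMB judges that continuing carries an unreasonable risk, no further randomized or crossover subject is treated pending investigation, whether or not the event was anticipated.*

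Procedure-related events are added because Section 9.8.1 lists neurological deficits under that heading, so a serious deficit attributed to the procedure would otherwise escape the rule. Naming the DSMB settles who decides, which 10.1 leaves to an unspecified 'we'. Leave 9.11 unchanged.

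The cost is one paragraph in an amendment, with no effect on sample size or visits. The downside is a possible extra pause, only where continuing has already been judged an unreasonable risk. For haemorrhage, the chance of at least one bleed among 10 treated is an upper bound on the chance of such a pause: 5-18% at 0.5-2%, and 61% at 1/11. Pauses for other serious related events would add to this, and the protocol gives no rate for them.
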